5.5 Covariates and strata

Diagnosis cohort (DLBCL, FL, CLL/SLL) will be used as a covariate for analyses that are pooled across diagnosis cohorts in the Dose Expansion part, where appropriate.

The following covariates may be summarized and/or used in analyses as appropriate:

- Diagnosis cohort (DLBCL, HGBCL, PMBCL, FL, MCL, MZL, SLL, or CLL for Dose Escalation part; DLBCL, FL, or CLL for Dose Expansion part)
- Age (continuous or <65 vs. 65+ years)
- Race (categorized into no more than 4 groups, such as Caucasian, Asian, Black, or Other)
- Eastern Cooperative Oncology Group (ECOG) score at screening (actual score or 0-1 vs. 2-4)
- Presence of constitutional symptoms at Screening
- Body mass index (BMI) at screening (continuous or categorized as <18.5, 18.5-24.9, 25.0-29.9, and 30.0+)
- Number of prior anti-cancer therapies (categorized as 1, 2, 3, 4+, or grouped into smaller categories)
- Time from last anti-CD20 therapy till first dose of GEN3009, in days
- Geographic location, as summarized below
- Prior CAR-T exposure category (exposure vs. no exposure)
- Overall MRD negativity status, as described in Section 5.2.4.
- Overall presence or absence of anti-drug antibodies, as described in Section 11.8
- Presence or absence of anti-drug antibodies at Baseline
- Refractory or relapsed to the last line of prior anti-lymphoma therapy
- Refractory or relapsed to the most recent prior anti-CD20 therapy
- Refractory or relapsed to the most recent prior anti-CD20 therapy, when that is the most recent prior anti-lymphoma therapy

- Prior autologous stem cell transplant status

Missing values of covariates will not be imputed. Subjects will be excluded from subgroup analyses, etc. as appropriate.

Trial sites, countries and regions

Subjects will be recruited from across Europe and North America.

Trial sites or countries will be pooled to main regions and regions using the "Standard Country or Area Codes for Statistical Use provided by the Statistics Division of the United Nations Secretariat" [1] as per Appendix II.

In general, Main Region may be used as a covariate. Region may also be considered as a covariate. Regions with <5 subjects will be combined within Main Region, combining the smallest regions with others the same size, and the next larger size if necessary, until each region or pooled region has 5 or more subjects.

5.6 Subgroups

The covariates listed in Section 5.5 may be used in exploratory subgroup analyses during the Dose Expansion part, if sample size allows.

5.7 Missing data

In general, missing data will not be imputed and the data will be analysed as they are recorded.

No imputation of response will be performed.

Pharmacokinetic concentrations below the lower limit of quantification (LLOQ) will be imputed as LLOQ/2 for analyses, as described in Section 13.

Partial or missing dates and times

For incomplete start dates of a medication, event, or medical condition:

- A completely missing start date, coupled with an end date that may be after the first dose of trial medication, will be imputed as starting on the date of first dose of trial medication. (An *end date that may be after the first dose* is considered to be: a completely missing end date, an end date whose partial information permits it to be on or after the first dose, or a complete end date that is on or after the first dose).
- A partially missing start date, that may be on the date of first dose of trial medication (either the month and year are equal to the month and year of the first dose, with missing day, or the years are equal and the day and month is missing), that does not have a partial or complete end date indicating it end before the first dose, will also be imputed as starting on the date of the first date of trial medication.
- A completely missing start date, coupled with an end date that is before the first dose, will be set equal to the subject's birth date.
- A partially missing start date, either coupled with an end date that is before the first dose or whose partial information indicates that it is before the first dose, will be imputed as the earliest possible date (first day of the month, when month and year are present; January 1st, if only the year is present).

For incomplete start dates of a medication, event, or medical condition:

- Where possible, and the end date is completely missing, the event, medication, or condition will be assumed to be ongoing. (If necessary for computations of duration, the last known alive date may be used as an end date).
- For partially missing dates, the latest possible date will be used (the end of the month, when month and year are present; December 31st, if only the year is present).

Similarly, for incomplete start times:

- For events, medications, or conditions beginning on the date of first dose of trial medication, the start time will be imputed as the time of the start of the first dose of trial medication, unless partial information indicates otherwise, in which case it will be imputed as 00:00.
- All partial or missing start times on other days will be imputed as the earliest possible time.

Incomplete end times will be imputed as 23:59.

5.8 *Observation and analysis times*

Subject information may be presented by cycle day or study day, as appropriate.

Study days

Study day is defined as the number of days between the first dose of trial medication and a particular date, and is calculated as:

- Study day = Assessment date – Date of first dose of trial medication, where assessment date is before the date of first dose
- Study day = Assessment date – Date of first dose of trial medication + 1, where assessment date is on or after the date of first dose

Therefore, the date of the first dose of trial medication will be Day 1, and the day immediately prior will be Day -1.

Cycle days

Cycle day is presented by both cycle number and day number, where C2D1 represents Day 1 of Cycle 2. The first dose of trial medication for a given cycle is considered Day 1 of that cycle, and cycle day in general are calculated as for study day:

- Cycle day = Assessment date – Date of first dose of trial medication + 1, where assessment date is on or after the date of first dose

Cycle day is not defined for dates prior to the first dose of trial medication, or for dates greater than 28 days after the last dose of trial medication. In infrequent cases, a new cycle might be delayed; the days between the 28th day of the last cycle and the 1st day of the new cycle will be considered off-cycle days, and cycle day will not be defined. If a new cycle starts slightly earlier than the planned day for any reason, the first day of dosing in that cycle will be considered Cycle x Day 1, and the prior cycle will have <28 days.

Trial periods

For the Dose Escalation part only, the DLT assessment period (also referred to as the DLT observation period) is defined as 28 days from Cycle 1 Day 1, as per protocol 7.1. Therefore, this period will run from Cycle 1 Day 1 through Cycle 1 Day 28.

The trial participation period is divided into three mutually exclusive segments:

- The pre-treatment period includes information collected from the date of informed consent until the day prior to the first dose of trial medication. (Subjects not receiving trial medication will remain in the pre-treatment period for the duration of their participation.)
- The on-treatment period begins on the date of the first dose of trial medication, and stops 4 weeks (i.e. 28 days) after last dose of trial medication.
- The post-treatment period begins at end of on-treatment period + 1 day

If incomplete data makes it impossible to definitively assign an observation to one of these periods, the data will be conservatively assigned to the on-treatment period.

Definition of analysis time points or time windows

Data reported on the CRF will be assigned to analysis visits as follows, where 'visit' refers to visit name or cycle day, as applicable. Data will be listed by nominal visit, as recorded on the CRF, and summarized in tables and figures using the analysis day:

- a) Visits prior to the date of first dose of trial medication will be assigned to the Screening visit.
- b) Scheduled post-baseline visits other than end of treatment or end of trial visits will be assigned to the nominal visit.
- c) Regularly scheduled assessments occurring at an unscheduled visit, end of treatment visit, or end of trial visit will be assigned to the closest scheduled visit (or the later of the two visits, if equidistant between scheduled visits). For example, if a subject completes Cycle 3 Day 8 visit and returns 2 days later for an end of treatment visit, the assessments collected at that visit would be assigned to Cycle 3 Day 11.
- d) If >1 assessment of a certain type is assigned to a given analysis visit:
 - i. If only 1 assessment is non-missing, the non-missing results will be summarized.
 - ii. If >1 assessment is non-missing, and only 1 assessment is within the visit window, the assessment within the visit window would be summarized.
 - iii. If >1 non-missing assessments are within the visit window, and one was collected at the actual visit, that assessment will be used. Otherwise, the one that is closest to the planned time of the visit will be used.

5.9 *Multiple Comparison/Multiplicity*

No multiplicity adjustment is planned.

6 Subject Accounting and Disposition

6.1 *Subject accounting*

The number and percentages of subjects in each analysis set as defined in Section 4 will be presented by dose level cohort or diagnosis cohort (as appropriate), region, country and site.

6.2 *Disposition and withdrawals*

The number and percentage of subjects will be summarized by dose level cohort or diagnosis cohort (as appropriate), including:

- Subjects initiating Cycle 1, 2, 3 ...
- Subject status by trial period: Not yet begun treatment, On treatment, Post-treatment but remaining on trial, and Withdrawn from Trial
- Death by trial period and cycle, if applicable
- Reasons for discontinuation, overall and by trial period

The time course of withdrawal from the trial will be presented by means of an incidence curve.

An overall listing of all subjects screened, including site, country, informed consent date and version, screening number, DNA informed consent flag, and analysis set flags will be provided. Additionally, a separate listing will be provided for subjects who were successfully screened but not treated, as well as a listing of screen failures. A listing of inclusion and exclusion criteria not met, for subjects in the FAS, will also be provided.

6.3 *Protocol deviations*

Important protocol deviations will be detailed in the Protocol Deviation Plan.

All violations of the inclusion criteria will be summarized by cohort and trial site for the FAS.

All subjects with protocol deviations as specified above will be listed.

7 Demographics and Background Characteristics

Demographic and baseline characteristics, as specified below, will be presented descriptively.

7.1 *Demographics*

The following demographic characteristics will be presented:

- Sex
- Age (years), as entered on the CRF, continuously and categorized as <65 and 65+ years
- Race and ethnic origins, as entered on the CRF
- Weight (kg) at baseline
- Height (cm) at baseline

7.2 *Disease characteristics*

The following baseline characteristics will be presented:

- Primary diagnosis (DLBCL, FL, CLL/SLL, etc.)
- Disease status at Screening
- ECOG performance status at screening
- Ann Arbor stage (for B-cell NHL) or Binet stage (for CLL/SLL) at initial diagnosis
- Time from initial diagnosis, in months (as per Section 5.4)
- Time from most recent recurrence/relapse or progression to first dose of GEN3009, in months (if applicable)

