9.3.6 Survival Status

Survival status will be assessed every 3 months via telephone contact, email, or on-site visit, after the last administration of GEN3009 and/or GEN3013 and will continue until the subject dies or withdraws from the trial. Data will be collected as reported by the subject regarding disease status, new anti-lymphoma treatment, any other malignancy other than the disease under study (ie, a second primary malignancy), and survival status, if available. If the subject is not available for this assessment, the response should be entered as “lost to follow up” ([Section 8.4](#)).

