Overall survival (OS) will be calculated in days as:

OS = date of death from any cause – date of first dose of investigational treatment + 1

Subjects not known to have died will be censored at the last date known to be alive.

Time to next anti-lymphoma treatment (TTNT) will be calculated in days as:

TTNT = date of first recorded administration of subsequent anti-lymphoma therapy – date of first dose of investigational treatment + 1

In the absence of recorded subsequent anti-lymphoma therapy, subjects will be censored at the last non-missing disease assessment.

Time to response (TTR) will be calculated in days as:

TTR = date of first response – date of first dose of GEN3009 + 1

TTR will only be calculated for those subjects achieving CR or PR.

Sustained MRD negative response will be calculated as described in Section 10.2.8.

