9.2 Subsequent Anti-Cancer Therapies

Subsequent anti-lymphoma therapies (initiated after first dose administration of GEN3009) will be categorized using WHODRUG, and summarized by ATC Level 2 and preferred term.

The time to next anti-lymphoma therapy will be summarized as per Section 10.2.5. Missing or partly missing stop dates will be imputed using the rules defined in Section 5.7, where applicable.

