Progression documented between scheduled visits	Earliest of: - Date progression assessment showing new lesion (if progression is based on new lesion) - Date of last progression assessment	Progressed
No progression	Date of last progression assessment with no documented progression	Censored
Treatment discontinuation for undocumented progression	Date of last progression assessment with no documented progression	Censored
Treatment discontinuation for toxicity or other reason	Date of last progression assessment with no documented progression	Censored
Next anti-lymphoma treatment started	Date of last progression assessment with documented non-progression before start of new treatment	Censored
Death before first PD assessment	Date of death	Progressed
Death between adequate assessment visits	Date of death	Progressed
Death or progression after more than one missed visit	Date of last progression assessment with documented non-progression	Censored

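### The SAP's incomplete-date rule can place the start of subsequent anti-lymphoma therapy on the first-dose date, giving a TTNT of 1 day, PFS censored at or before Day 1 and a negative DoR

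*SAP*

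**What the plan says.** **SAP 5.7, first block.** It is introduced by "For incomplete start dates of a medication, event, or medical condition" and sets the start to the first-dose date in these cases:

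- Wholly missing date: "A completely missing start date, coupled with an end date that may be after the first dose of trial medication, will be imputed as starting". The value used is the first-dose date. An end date that is itself missing counts as one that may be later.
- Partial date: this covers a missing day where month and year equal those of first dose, "or the years are equal and the day and month is missing". Unless the end date shows that the record ended before first dose, such a date "will also be imputed as starting on the date of the first date of trial medication".

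**SAP 5.7, second block.** It carries the same heading about start dates but uses the latest possible date, which is 31 December when only the year is known. Its content suggests that it was meant for end dates.

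**SAP 9.2.** Subsequent anti-lymphoma therapies are those begun after the first GEN3009 dose, and they are coded in WHODRUG. On incomplete dates the section says: "Missing or partly missing stop dates will be imputed using the rules defined in Section 5.7, where applicable".

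**SAP 5.4.** "TTNT = date of first recorded administration of subsequent anti-lymphoma therapy", minus the first-dose date, plus 1.

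**SAP Appendix I.** When a next anti-lymphoma treatment has started, PFS and DoR are censored at: "Date of last progression assessment with documented non-progression before start of new treatment". Protocol 11.8.4 likewise counts a PFS event only if it comes before new anti-neoplastic therapy, and leaves the detailed censoring rules to the SAP.

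**Protocol 9.3.6.** In survival follow-up, every 3 months by telephone, email or visit: "Data will be collected as reported by the subject regarding disease status, new anti-lymphoma treatment".

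**The concern.** Moving an uncertain start date to first dose is cautious for adverse events and concomitant drugs, because it keeps the record inside the treatment period. For a therapy that by definition follows trial treatment, the same rule is neither cautious nor possible. It creates a next-therapy event on the first day of the trial.

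The error then spreads. TTNT takes the imputed date directly. PFS and DoR take it through the censoring rule, which looks for the last scan before the new therapy; with a first-dose start, only the screening scan is left. A progression that was really observed, perhaps the one that led to the new therapy, drops out of the analysis. Follow-up reports given by the subject are a plausible source of incomplete dates.

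**Working it through.** The plan states no figure on this point, so there is nothing to reproduce. The check applies the SAP 5.7 rules to an example and carries the result through SAP 5.4 and Appendix I.

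**Inputs from the documents**

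- TTNT = therapy start - first dose + 1 (SAP 5.4).
- PFS runs from Cycle 1 Day 1, with + 1; DoR = event or censoring date - first response + 1 (SAP 5.4).
- The screening scan falls 0 to 21 days before Cycle 1 Day 1 (Protocol Table 29).
- Expansion cohorts have 20 subjects per indication (SAP 3.4).

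**Assumed example.** First dose 16 March 2020 (Day 1); response at Week 6 (Day 43); last scan without progression Day 126; last trial dose Day 162; progression Day 169; new therapy Day 183.

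**True values**

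- TTNT 183 days
- PFS event on Day 169
- DoR = 169 - 43 + 1 = 127 days

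**What SAP 5.7 gives for each kind of incomplete start date**

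| Recorded start | First block | Second block, read literally |
|---|---|---|
| Wholly missing, end missing or possibly later | first dose | not addressed as a start date |
| Year only, same year as first dose | first dose | 31 December |
| Day missing, same month and year as first dose | first dose | end of that month |
| Year only, later year | no rule | 31 December of that year |
| Day missing, later month | no rule | end of that month |

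**Consequences where the start becomes the first-dose date**

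- TTNT = 0 + 1 = 1 day, against a true 183.
- PFS is censored at the screening scan. A scan 0 days before dose gives -0 + 1 = Day 1; a scan 21 days before gives -21 + 1 = -20. The Day 169 progression follows the imputed therapy start and is not counted.
- DoR: the scan precedes the Week 6 response by 42 to 63 days, so DoR = -42 + 1 = -41 to -63 + 1 = -62 days.

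**The competing answer.** Under the second block, a year-only date in 2020 becomes 31 December 2020 and TTNT is 291 days. One recorded date therefore gives 1 or 291 days, depending on which block the programmer follows.

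**Reach of the year-only case.** If first-dose dates are spread evenly over the calendar year (assumed), a therapy starting t days after first dose falls in the same year with probability 1 - t/365:

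- t = 90: 75%
- t = 180: 51%
- t = 270: 26%
- t = 365 or more: 0%

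These are shares of year-only dates, not of subjects.

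**Weight of one subject.** 1/20 = 5%. One affected subject takes the TTNT curve to 19/20 = 95% on Day 1 and leaves 19 subjects in the PFS risk set.

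**The case against.** The best defence is that SAP 9.2 does not send start dates to 5.7. It names only stop dates, adds a where-applicable qualifier, and repeats the sentence used in 9.1 for concomitant drugs. Its own definition of subsequent therapy conflicts with a first-dose start. A careful programmer would see the conflict and ask. This is right as a reading of 9.2: the effect comes from the general wording of 5.7. But TTNT needs a start date, no other rule supplies one, and 5.7 makes no exception.

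A second defence is that such dates may be rare. Protocol 8.3 places the safety follow-up visit before new therapy, the visit schedules collect new anti-cancer treatment during follow-up, and Protocol 12.2 provides for data queries. These measures should resolve many dates. The documents give no rate, so rarity can be neither shown nor excluded.

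A third is that the endpoints are descriptive. That stands and limits the weight of the point. TTNT is not among the endpoints in Protocol Tables 17 to 20; it enters as a secondary endpoint in SAP 10.

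Three stronger readings are tempting but not supported:

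- That every year-only date moves to first dose. The first block requires the year to equal the first-dose year.
- That DoR is simply censored at baseline. Its clock starts at response, so the result is a negative duration.
- That the day after the last trial dose is a sufficient lower bound. In the example it gives Day 163, PFS is still censored at Day 126 (DoR 126 - 43 + 1 = 84), and the Day 169 progression is still lost.

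**Conclusion.** The rule is wrong as written for subsequent anti-lymphoma therapy. Following it gives a start date that contradicts SAP 9.2, a TTNT of 1 day, PFS censored at or before Day 1 and, in a responder, a negative DoR. The duplicated heading also lets one year-only date yield two different answers.

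The scope is limited. Under the first block, the exposed records are wholly missing start dates whose end date is missing or may be on or after first dose, year-only dates in the first-dose year, and day-missing dates in the first-dose month. TTNT, PFS and DoR are affected; the definitions of ORR and CR rate do not use this date. A reader might infer that the trial's main efficacy result is at risk, but the documents do not support that, and no formal hypothesis is tested.

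The consequence per subject follows from the SAP's formulas; the Week 6 response is an assumption used to size the DoR error. The number of subjects is unknown, and the same-year shares rest on assumed even enrolment. With 20 per cohort, even one such record is visible. The point should be corrected before PFS, DoR and TTNT are analysed.

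**What to change.** 1. **Give subsequent therapy its own rule in SAP 5.7.** Exclude it from the first-dose rule. Impute an incomplete start as the latest of: (a) the earliest date consistent with the recorded part; (b) the day after the last trial-drug dose; (c) the day after the last visit or contact at which no new therapy was recorded. Do not go beyond the contact at which the therapy was first reported. In the example, if the Day 169 visit recorded no new therapy, (c) gives Day 170: TTNT is 170 days against a true 183, and the Day 169 progression is kept.

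2. **Flag and list every imputed date, and add one sensitivity analysis.** Repeat PFS and DoR with the latest compatible start date. This is needed because, where no visit supports (c), an early imputed date can still censor the progression that prompted the change of therapy.

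3. **Correct the wording.** Change the heading of the second block in 5.7 to refer to end dates, and make the cross-reference in 9.2 refer to start dates.

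The cost is a few sentences in the SAP, a few lines of programming and one sensitivity run. No additional data collection is needed.

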7.3 General medical history

The diseases are coded according to MedDRA, and will be classified as follows:

- Previous medical conditions, i.e. medical conditions that stopped prior to start of treatment
- Ongoing (concomitant) medical conditions, i.e. medical conditions still present after start of treatment

The frequency of diseases recorded from medical history will be presented after classification into previous and concomitant conditions by system organ class (SOCs) as well as the frequencies of preferred terms (PT) within each SOC.

Medical history will be summarized overall, and separately for previous medication conditions and ongoing medical conditions

